## **8.3 Randomization (Day 1), Visit 5**

- Confirm eligibility by reviewing inclusion/exclusion criteria ([Section 5](#))
- Body weight (pre-dialysis)
- Changes to medical/surgical history
- Physical examination
- Vital signs (pre-dialysis)
- ECG evaluation
- Clinical laboratory tests (pre-dialysis)
- Serum pregnancy test, if applicable
- FGF-23, Ca x P product and exploratory biomarker sample (pre-dialysis)
- Dispense study drug or active control
- Adverse event reporting
- Review prior/concurrent medications

## **8.4 Treatment Period (Days 8 and 15 $\pm$ 5), Visits 6 and 7**

- Vital signs (pre-dialysis)
- Serum phosphorus (pre-dialysis)

- Adverse event reporting
- Return/accountability of study drug or active control (Day 8, Visit 6 only)
- Dispense study drug (Day 8, Visit 6 only), if applicable
- Review concurrent medications

**8.5 Treatment Period (Days 29 ± 5 and 57 ± 7), Visits 8 and 9**

- Vital signs (pre-dialysis)
- Return/accountability of study drug or active control
- Dispense study drug or active control, if applicable
- Serum phosphorus (pre-dialysis)
- Adverse event reporting
- Review concurrent medications

**8.6 Treatment Period (Day 85 ± 7), Visit 10**

- Body weight (pre-dialysis)
- KDQOL survey
- DSI survey (for English speakers only)
- Vital signs (pre-dialysis)
- ECG evaluation
- Clinical laboratory tests (pre-dialysis)
- Serum pregnancy test, if applicable
- FGF-23, Ca x P product and exploratory biomarker sample (pre-dialysis)
- Return/accountability of study drug or active control
- Dispense study drug or active control, if applicable
- Adverse event reporting
- Review concurrent medications

**8.7 Treatment Period (Days 120 and 155 ± 7), Visits 11 and 12**

- Vital signs (pre-dialysis)
- Return/accountability of study drug or active control
- Dispense study drug or active control, if applicable
- Serum phosphorus (pre-dialysis)
- Adverse event reporting
- Review concurrent medications

**8.8 End of 26-week Treatment Period and start of Randomized Withdrawal Period (Day 183 ± 7), Visit 13**

- Randomization #2
- Body weight (pre-dialysis)
- KDQOL survey
- DSI survey (for English speakers only)
- Physical Examination
- Vital signs (pre-dialysis)
- ECG evaluation
- Clinical laboratory tests (pre-dialysis)
- Serum pregnancy test, if applicable
- FGF-23, Ca x P product and exploratory biomarker sample (pre-dialysis)
- Return/accountability of study drug or active control
- Dispense study drug or active control, if applicable
- Adverse event reporting
- Review concurrent medications

**8.9 Randomized Withdrawal Period (Days 197, 211, 225, 239 and 253 ± 7), Visits 14, 15, 16, 17 and 18**

**Subjects in the active control group do not have Visits 14, 16 and 18.**

- Vital signs (pre-dialysis)
- Serum phosphorus (pre-dialysis)
- FGF-23, Ca x P product and exploratory biomarker sample (Days 211 and 239 ± 5, Visits 15 and 17 only)
- Dispense study drug or active control at Visits 15 and 17 only, if applicable
- Return/accountability of study drug or active control
- Adverse event reporting
- Review concurrent medications

**8.10 End of Randomized Withdrawal Period and start of Safety Extension Period (Day 267 ± 7), Visit 19**

- Body weight (pre-dialysis)
- KDQOL survey
- DSI survey (for English speakers only)
- Physical Examination
- Vital signs (pre-dialysis)

- ECG evaluation
- Clinical laboratory tests (pre-dialysis)
- Serum pregnancy test, if applicable
- FGF-23, Ca x P product and exploratory biomarker sample (pre-dialysis)
- Return/accountability of study drug or active control
- Dispense study drug or active control, if applicable
- Adverse event reporting
- Review concurrent medications

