#### 4.1.1 Treatments Administered

At randomization (Visit 5), patients will be randomized to either tenapanor or the active control group. Patients randomized into the active control group will receive sevelamer carbonate for the entire 52-week study period. Dose of sevelamer will be adjusted per standard of care using the package insert for guidance.

Patients randomized into the tenapanor group will receive tenapanor at a dose of 30 mg bid. Tenapanor will be taken twice daily; just prior to breakfast and dinner. Tenapanor is supplied as 10 mg tablets; each dose of one to three tablets bid will achieve total daily doses of 20, 40, or 60 mg tenapanor.

The dose of tenapanor may be down titrated or up titrated to a max of 30 mg bid in a step-wise fashion based on serum-phosphorus levels and/or GI tolerability (detailed in [Section 6.1.3](#)). Down-titration can go from 30 mg bid to 20 mg bid and 20 mg bid to 10 mg bid. Dose escalation can go in 10 mg bid increments to a maximum dose of 30 mg bid.

On dialysis days, patients on HD should **not** take study drug at the meal prior to dialysis and instead take it before another meal. If a meal is skipped, the dose should be taken with another meal during the day or at around the time that the meal would have been consumed. Active control (sevelamer carbonate) will be taken based on standard of care using the package insert for guidance.

During the randomized withdrawal period, patients in the tenapanor group only will be randomized to either remain on their current dose of tenapanor or receive placebo in a 1:1 ratio.

Placebo will be administered PO during the randomized withdrawal period only for patients randomized into placebo from the tenapanor group. The same number of tablets as the last dose of tenapanor during 26-week treatment period will be administered to the placebo group. Patients from the active control group will not enter the randomized withdrawal period; they will continue to receive sevelamer carbonate per standard of care for the entire 52-week study period.

During the safety extension period, patients on tenapanor will continue at their same dose. Patients on placebo will continue with their same dose from the end of the 26-week treatment period. Titration is allowed as described for the 26-week treatment period.

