### **9.2 Determination of Sample Size**

Approximately five hundred sixty (560) male and female patients with end stage renal disease (ESRD) on chronic maintenance hemodialysis (HD) 3 times a week for a minimum of 3 months or peritoneal dialysis (PD) for a minimum of 6 months will be enrolled in this study. Patients will be randomized in a 3:1 ratio to receive either tenapanor (~420 patients) or active control (~140 patients). Those patients in the tenapanor group will be randomized at the end of the 26-week treatment period to enter into the randomized withdrawal period to either remain on their current dose of tenapanor or placebo in a 1:1 ratio.

For the primary efficacy analysis, a sample size of 146 patients (73 patients/group) in the 12-week randomized withdrawal period is expected to provide more than 95% power to detect a difference between tenapanor and placebo treatment in the change in serum phosphorus from the end of the 26-week treatment period to the end of the 12-week randomized withdrawal period or the endpoint visit for this period, between the tenapanor treatment and placebo. This calculation is based on a two-sample t-test with a two-sided significance level of  $\alpha=0.05$ , an assumed treatment difference of 1.0 mg/dL and a common standard deviation of 1.6 mg/dL. This sample size (560) allows for a 30% dropout rate, meaning 30% of patients will not complete the 26-week treatment period. This sample size also assumes at least 50% of patients in the tenapanor group will be considered responders in the 26-week treatment period, i.e., patients who achieves at least a 1.2 mg/dL reduction from baseline to the end of the 26-week treatment period.

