**Safety Analysis Set:**

All patients who receive at least one dose of study drug (tenapanor or placebo) or active control for the individual study period will be included in the safety analysis set. Such patients will be analyzed according to the treatment actually received.

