#### 9.4.8 Safety Analyses

Safety analyses include summaries for adverse events, safety laboratory tests, vital signs, body weights, 12-lead ECGs, and physical examinations. These summaries will be provided for each study period separately.

Adverse events will be coded using the Medical Dictionary for Regulatory Activities (MedDRA). Summary tables and listings will be provided by system organ class and preferred term for each treatment (including dose, if applicable) group for treatment-emergent adverse events (TEAEs). Actual values and change from baseline values for clinical laboratory tests, vital signs, body weights, and ECGs will be summarized by treatment (including dose, if applicable) group for each visit. The number and percentage of patients in each physical examination category will be presented by treatment (including dose, if applicable) group for each visit.

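### Extension-period safety tables put continuous tenapanor users and former placebo patients who restart it in one column, so long-term and restart adverse-event rates cannot be read separately

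*Combined protocol and SAP*

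**What the plan says.** At Visit 13 the tenapanor group is re-randomised 1:1 to stay on drug or receive placebo for up to 12 weeks (Sections 4.1 and 6.1.4). Section 4.1 says that everyone who enrols in the open-label extension receives tenapanor. Section 4.1.1 says of the former placebo arm: "Patients on placebo will continue with their same dose from the end of the 26-week treatment period"; titration is then allowed. The usual switch point is Visit 19, which Section 8.10 heads "End of Randomized Withdrawal Period and start of Safety Extension Period (Day 267 ± 7), Visit 19". Patients with serum phosphorus of 9 mg/dL or more in the withdrawal period may move over earlier (Sections 4.1 and 5.4; footnote g to the Schedule of Events).

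The Safety Analysis Set in Section 9.3 is defined per study period, with the rule "Such patients will be analyzed according to the treatment actually received". Section 9.4.8 plans summaries of adverse events, laboratory tests, vital signs, weight and ECGs by treatment group (including dose, if applicable), and adds: "These summaries will be provided for each study period separately". No section provides a split by Randomization #2 arm, by treatment sequence or by time since restart. Treatment-emergent events are named but not defined in relation to a restart.

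**The concern.** In the extension, tenapanor as the treatment received covers two different exposures. One group has taken the drug for 38 weeks without a break. The other took it for 26 weeks, was off it for up to 12, and is starting again. The split by dose does not separate them, because restarters resume the dose level they held at Week 26.

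This matters because safety over up to 52 weeks is a primary objective (Section 3.1) and the long-term safety comparison with sevelamer is a secondary one (Section 3.2). Sevelamer patients have no planned interruption, so any effect of restarting enters only the tenapanor side. Section 2.5 describes softer stools and higher stool frequency as expected pharmacology, so a recurrence on restarting is plausible. A single column would then serve neither question: it overstates the event rate under continuous use and understates the rate on restarting. Randomization #2 already defines the two groups, but the planned tables do not use it.

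**Working it through.** **1. Confirm the plan's own figures (Section 9.2).** The plan says that "a sample size of 146 patients (73 patients/group) in the 12-week randomized withdrawal period is expected to provide more than 95% power", with "an assumed treatment difference of 1.0 mg/dL and a common standard deviation of 1.6 mg/dL", two-sided alpha 0.05.
- Standardised difference: 1.0 / (1.6 × √(2/73)) = 1.0 / 0.2648 = 3.776.
- Normal approximation: Φ(3.776 − 1.960) = 96.5%. The noncentral t with 144 df gives 96.3%. Both agree with the stated power.
- Head count: 560 × 3/4 = 420 on tenapanor. With 30% dropout, 420 × 0.70 = 294 complete Week 26. With 50% responders, 294 × 0.50 = 147, against 146 stated.

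This check only establishes the head count used below; the sample-size calculation is not in question.

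**2. Composition of the extension column.** The 1:1 re-randomisation gives 294 / 2 = 147 per arm. The share entering the extension is not given, so these entry rates are assumptions:

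| Continuing arm entering | Placebo arm entering | Restarters' share s |
|---|---|---|
| 100% | 100% | 50% |
| 90% | 50% | 73.5 / 205.8 = 36% |
| 70% | 90% | 132.3 / 235.2 = 56% |

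**3. Exposure.** Day 183 is Week 26 (182/7), Day 267 is Week 38 (266/7) and Day 365 is Week 52 (364/7). A placebo patient who completes the withdrawal period can have at most 26 + 14 = 40 weeks on tenapanor. At most about 147 patients can have 52 continuous weeks.

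**4. Effect on the displayed rate.** Pooled rate = s × restart rate + (1 − s) × continuing rate. The documents give no event rates. With an assumed 5% in continuing patients:

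| Assumed restart rate | s = 36% | s = 50% | s = 56% |
|---|---|---|---|
| 5% | 5% | 5% | 5% |
| 15% | 8.6% | 10% | 10.6% |

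In the second row the column shows 1.7 to 2.1 times the continuing rate and about 0.6 to 0.7 times the restart rate. In the first row there is no distortion.

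**5. Precision cost of splitting.** The 95% half-width at a 10% rate is 1.96 × √(0.1 × 0.9 / n): ±4.85 points with n = 147 and ±3.43 points with n = 294.

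**The case against.** **The governing SAP may already split the columns.** Section 9.1 refers to a separate SAP that prevails over the protocol, and its text is not in the document reviewed. Section 9.4.8 also does not spell out the extension's treatment groups, so a layout by sequence would not contradict it. This stands as a limit on certainty. It does not remove the stated as-received rule, and nothing supplied replaces that rule for the extension.

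**The size is unknown.** Restarters tolerated 26 weeks, resume a dose reached after titration was allowed, and have a stool change counted only if they find it bothersome (Section 7.3.6.1). The restart effect may be small or absent. This stands: the rates above are illustrations, not predictions.

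**Stronger readings that the documents do not support.**
- A reader might infer that the trial is likely to find tenapanor falsely worse than sevelamer. Section 9.4.8 plans descriptive summaries, with no confidence interval or test against sevelamer, so there is no planned decision to get wrong.
- A reader might infer that restart events would go unreported. Listings and by-visit summaries also cover the extension; what is missing is a summary that separates the groups.
- A reader might infer that long-term harm relative to sevelamer would be hidden. If restarting adds events, the distortion in that comparison runs against tenapanor.
- A reader might take the extension column as exactly Weeks 38 to 52 with exactly half restarting. Early entry is allowed and entry shares are not stated, so both are approximations. Early entry adds to the mixing.

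**Conclusion.** The concern holds as a gap in the planned presentation. Under Sections 9.3 and 9.4.8 as written, continuous users and restarters share one extension-period tenapanor column. Up to 147 of about 294 patients in it would be restarters (36% to 56% under the entry rates assumed). If restarting brings on events, that column describes neither continuous use nor restarting; at assumed rates of 5% and 15% it would show about 8.6% to 10.6%. If restarting adds nothing, there is no bias.

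The conclusion rests on three points: former placebo patients do enter the extension, as Section 4.1.1 provides; the separate SAP does not already split the column; and restarting has some effect on event rates. Only the first is stated in the documents. It also sits awkwardly with the synopsis and Section 4.1, whose eligibility sentence for completers can be read as covering only patients randomised to tenapanor. Those passages must be reconciled.

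**What to change.** In Section 9.4.8, and in the separate SAP if it does not already do so:
- Present all extension-period safety summaries by Randomization #2 arm (tenapanor-to-tenapanor and placebo-to-tenapanor) beside sevelamer.
- Count events in the placebo-to-tenapanor arm from each patient's actual extension start date, because entry may precede Visit 19.
- Use the tenapanor-to-tenapanor column for the long-term comparison with sevelamer, and report the other column as restart experience.
- Keep the pooled tenapanor column as a supplement, and report exposure by sequence.
- Reconcile the wording on extension entry in the synopsis and Section 4.1 with Section 4.1.1.

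The cost is extra columns in existing tables, with no new data or visits. Intervals in the split columns are wider, as shown in the working. Because the pooled column is retained, no information is lost.

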**8.11 Safety Extension Period (Days 281, 309, 337 ± 7), Visits 20, 21, 22**

- Pre-dialysis body weight (Day 337, Visit 22 only)
- Vital signs (pre-dialysis)
- Serum phosphorus (pre-dialysis)
- Return/accountability of study drug or active control
- Dispense study drug or active control, if applicable
- Adverse event reporting
- Review concurrent medications

**8.12 End of Study (Day 365 ± 7), Visit 23**

- Body weight (pre-dialysis)
- KDQOL survey
- DSI survey (for English speakers only)
- Physical Examination
- Vital signs (pre-dialysis)
- ECG evaluation
- Clinical laboratory tests (pre-dialysis)
- Serum pregnancy test, if applicable
- FGF-23, Ca x P product and exploratory biomarker sample (pre-dialysis)
- Return/accountability of study drug or active control
- Adverse event reporting
- Review concurrent medications

**8.13 Unscheduled visits**

Unscheduled visits, for missed scheduled visits or safety or tolerability related reasons are allowed. Procedures performed are at the discretion of the Investigator.

#### 8.14 Withdrawal Procedures

In the event of a patient's withdrawal, the Investigator will make every effort to complete all assessments performed at End-of-treatment visit on Day 365 (Visit 23). Withdrawn patients will be followed until resolution of any AEs or until the unresolved AEs are judged by the Investigator to have stabilized.

For the withdrawal criteria see [Section 5.4](#).

#### 8.15 Total Blood Volume Required for Study

**Table 8-1 Approximate Blood Volume per Completed Patient**

Test	Number of Samples	Volume (mL)	Total (mL)
Serology and FSH test (serum)	1	5	5
Hematology (blood)	6	3	18
Chemistry (serum) (includes serum pregnancy test)	6	7	42
Phosphorus / Calcium (serum)#	17	7	119
PTH (plasma)	8	4	32
FGF-23 (plasma)	8	8	64
Exploratory biomarker sample (serum and plasma)	8	13	104
Total volume	--	--	384

#Separate sample is only taken at specified times when no chemistry sample is taken

#### 8.16 Protocol Deviations

Patients must fully meet the following criteria in order to enroll in the study. In keeping with regulatory requirements, Ardelyx does not grant protocol waivers to inclusion/exclusion criteria.

A protocol deviation is defined as any intentional or unintentional change to, or noncompliance with, the approved protocol procedures or requirements. Deviations may result from the action or inaction of the patient, Investigator, or site staff. Examples of deviations include, but are not limited to:

- Failure to adhere to study exclusion and inclusion criteria
- Failure to comply with dispensing or dosing requirements
- Missed or out-of-window visits
- Failure to adhere to test requirements, including vital signs, laboratory tests, physical examinations, medical history; either tests not done, incorrect tests done, or not done within the time frame specified in the protocol

- Procedural deviations such as incorrect storage of study drug, failure to update the ICF when new risks become known, failure to obtain Institutional Review Board (IRB) approvals for the protocol and ICF revisions

A process for defining and handling protocol deviations will be established. Protocol deviations that effect the safety of a patient requires immediate notification of the Medical Monitor and Sponsor. The Investigator is responsible for seeing that any known protocol deviations are recorded and handled as agreed.

## **9 STATISTICAL CONSIDERATIONS**

### **9.1 Statistical Analysis Plan**

A formal statistical analysis plan (SAP) is provided separately. No changes are expected for the primary and secondary analyses. If the language in this protocol and the language in the SAP differ, the SAP governs. If additional analyses are performed or changes are made to the planned analyses after unblinding of the study data, such deviations will be documented in the clinical study report.

### **9.2 Determination of Sample Size**

Approximately five hundred sixty (560) male and female patients with end stage renal disease (ESRD) on chronic maintenance hemodialysis (HD) 3 times a week for a minimum of 3 months or peritoneal dialysis (PD) for a minimum of 6 months will be enrolled in this study. Patients will be randomized in a 3:1 ratio to receive either tenapanor (~420 patients) or active control (~140 patients). Those patients in the tenapanor group will be randomized at the end of the 26-week treatment period to enter into the randomized withdrawal period to either remain on their current dose of tenapanor or placebo in a 1:1 ratio.

For the primary efficacy analysis, a sample size of 146 patients (73 patients/group) in the 12-week randomized withdrawal period is expected to provide more than 95% power to detect a difference between tenapanor and placebo treatment in the change in serum phosphorus from the end of the 26-week treatment period to the end of the 12-week randomized withdrawal period or the endpoint visit for this period, between the tenapanor treatment and placebo. This calculation is based on a two-sample t-test with a two-sided significance level of  $\alpha=0.05$ , an assumed treatment difference of 1.0 mg/dL and a common standard deviation of 1.6 mg/dL. This sample size (560) allows for a 30% dropout rate, meaning 30% of patients will not complete the 26-week treatment period. This sample size also assumes at least 50% of patients in the tenapanor group will be considered responders in the 26-week treatment period, i.e., patients who achieves at least a 1.2 mg/dL reduction from baseline to the end of the 26-week treatment period.

### **9.3 Analysis Sets**

Four analysis sets are defined for this study: safety analysis set, intent to treat (ITT) analysis set, efficacy analysis set and per-protocol (PP) analysis set. These analysis sets will be determined for each study period separately (if applicable). The safety analysis set will be defined based on all patients enrolled in this study. All other three analysis sets will be defined based on those patients who are randomized to receive tenapanor in the 26-week treatment period.

**Safety Analysis Set:**

All patients who receive at least one dose of study drug (tenapanor or placebo) or active control for the individual study period will be included in the safety analysis set. Such patients will be analyzed according to the treatment actually received.

**Intent to Treat (ITT) Analysis Set:**

All patients who meet the study entry inclusion/exclusion criteria, receive at least one dose of tenapanor or placebo, and have at least one post treatment serum phosphorus assessment for the individual study period will be included in the ITT analysis set. For the 12-week randomized withdrawal period, patients will be analyzed according to the treatment group into which they were randomized. The ITT analysis set will be used for the analysis of all efficacy variables.

